9.4.3. Other Events that Require Accelerated Reporting to Sponsor

The following events also require reporting to the sponsor (or designee) within 24 hours of learning of the event:

Symptomatic Overdose of Study Drug: Accidental or intentional overdose of at least 2 times the intended dose of study drug within the intended therapeutic window, if associated with an AE

Pregnancy: Although pregnancy is not considered an AE, it is the responsibility of the investigator to report to the sponsor (or designee), within 24 hours of identification,

any pregnancy occurring in a female or female partner of a male, during the study or within 24 weeks of the last dose of study drug. Any complication of pregnancy affecting a female study patient or female partner of a male study patient, and/or fetus and/or newborn that meets the SAE criteria must be reported as an SAE. Outcome for all pregnancies should be reported to the sponsor

Adverse Events of Special Interest: All AESIs, serious and non-serious, must be reported within 24 hours of identification using the same reporting process as for SAE reporting, per Section 9.4.2.

Adverse events of special interest for evinacumab include the following:

- Anaphylactic reactions
- Allergic reactions and/or local injection site reactions that require medical treatment or consultation with another physician for further evaluation
- Increase in ALT or AST: ≥ 3 x ULN (if baseline < ULN), or ≥ 2 x baseline value (if baseline \geq ULN)
- Pregnancy
- Symptomatic overdose with IMP
- Neurocognitive events
- New onset of diabetes
- Pancreatitis

Adverse events of special interest for alirocumab include the following:

- Increase in ALT: ALT ≥ 3 x ULN (if baseline ALT < ULN), or ALT ≥ 2 x baseline value (if baseline ALT \geq ULN)
- Allergic events and/or local injection site reactions that require consultation with another physician for further evaluation
- Pregnancy
- Symptomatic overdose with IMP
- Neurologic events that require additional examinations/procedures and/or referral to a specialist
- Neurocognitive events
- Cataracts
- New onset of diabetes:

The definition of new onset of diabetes will be the following:

- Type 1 or type 2 diabetes treatment-emergent adverse event (TEAE) (grouping of MedDRA terms will be specified in the SAP)

and/or

- at least 2 values of HbA1c $\geq 6.5\%$ during the TEAE period

NOTE: For patients with only a single measurement available during the TEAE period, a single value $\geq 6.5\%$ will be considered and qualify the patient as new onset of diabetes by default.

For patients with several HbA1c measurements but only with the last one $\geq 6.5\%$, this single value $\geq 6.5\%$ will be considered and qualify the patient as new onset of diabetes by default

and/or

- At least 2 values of fasting plasma glucose ≥ 126 mg/dL (7.0 mmol/L)

NOTE: For patients with only a single measurement available during the TEAE period, a single value ≥ 126 mg/dL (7.0 mmol/L) will NOT be considered and will NOT qualify the patient as new onset of diabetes

For patients with several fasting plasma glucose measurements but only with the last one ≥ 126 mg/dL (7.0 mmol/L), this single value ≥ 126 mg/dL (7.0 mmol/L) will NOT be considered and will NOT qualify the patient as new onset of diabetes

9.4.4. Reporting Adverse Events Leading to Withdrawal from the Study

All AEs that lead to a patient's withdrawal from the study must be reported to the sponsor's medical monitor within 30 days.

9.4.5. Abnormal Laboratory, Vital Signs, or Electrocardiogram Results

The criteria for determining whether an abnormal objective test finding should be reported as an AE include:

- the test result is associated with accompanying symptoms, and/or
- the test result requires additional diagnostic testing or medical/surgical intervention, and/or
- the test result leads to a change in dosing (outside of protocol-stipulated dose adjustments), discontinuation from the study, significant additional concomitant drug treatment, or other therapy

Contact the medical monitor in the event the investigator feels that an abnormal test finding should be reported as an AE, although it does not meet any of the above criteria.

Repeating an abnormal test, in the absence of any of the above conditions, does not constitute an AE. Any abnormal test result that is determined to be an error does not require reporting as an AE.

Evaluation of severity of laboratory abnormalities will be assessed according to the scale outlined in Section 9.5.1.

9.4.6. Follow-up

Adverse event information will be collected until the patient's last study visit.

Serious adverse event information will be collected until the event is considered chronic and/or stable.

9.5. Evaluation of Severity and Causality

9.5.1. Evaluation of Severity

The severity of AEs will be graded according to the following scale:

- **Mild:** Does not interfere in a significant manner with the patient normal functioning level. It may be an annoyance. Prescription drugs are not ordinarily needed for relief of symptoms, but may be given because of personality of the patient.
- **Moderate:** Produces some impairment of functioning but is not hazardous to health. It is uncomfortable or an embarrassment. Treatment for symptom may be needed.
- **Severe:** Produces significant impairment of functioning or incapacitation and is a definite hazard to the patient's health. Treatment for symptom may be given and/or patient hospitalized.

If a laboratory value is considered an AE, its severity should be based on the degree of physiological impairment the value indicates.

Infusion Reactions

The severity of infusion reactions will be graded according to the following scale (semi-colon indicates "or" within description of the grade):

- **Mild:** Mild transient reaction; infusion interruption not indicated; intervention not indicated.
- **Moderate:** Therapy or infusion interruption indicated but responds promptly to symptomatic treatment (eg, antihistamines, NSAIDs, narcotics, IV fluids); prophylactic medications indicated for ≤ 24 hours.
- **Severe:** Prolonged (eg, not rapidly responsive to symptomatic medication and/or brief interruption of infusion); recurrence of symptoms following initial improvement; hospitalization indicated for clinical sequelae; life-threatening consequences; urgent intervention indicated; death.

Injection Site Reactions

The severity of injection site reactions will be graded according to the following scale (semi-colon indicates "or" within description of grade):

- **Mild:** Pain that does not interfere with activity; mild discomfort to touch; < 5 cm of erythema or induration that does not interfere with activity
- **Moderate:** Pain that requires repeated use of non-narcotic pain reliever > 24 hours or interferes with activity; discomfort with movement; 5.1 cm to 10 cm erythema or induration or induration that interferes with activity

- **Severe:** Pain that requires any use of narcotic pain reliever or that prevents daily activity; significant discomfort at rest; > 10 cm erythema or induration; prevents daily activity; requires ER visit or hospitalization; necrosis or exfoliative dermatitis

9.5.2. Evaluation of Causality

Relationship of Adverse Events to Study Drug:

The relationship of AEs to study drug will be assessed by the blinded investigator, and will be a clinical decision based on all available information. The following question will be addressed:

Is there a reasonable possibility that the AE may have been caused by the study drug?

The possible answers are:

Not Related: There is no reasonable possibility that the event may have been caused by the study drug

Related: There is a reasonable possibility that the event may have been caused by the study drug

A list of factors to consider when assessing the relationship of AEs to study drug is provided in [Appendix 1](#).

The investigator should justify the causality assessment of each SAE.

Relationship of Adverse Events to Study Conduct:

The relationship of AEs to study conduct will be assessed by the blinded investigator, and will be a clinical decision based on all available information. The following question will be addressed:

Is there a reasonable possibility that the AE may have been caused by study conduct?

The possible answers are:

Not Related: There is no reasonable possibility that the event may have been caused by study conduct

Related: There is a reasonable possibility that the event may have been caused by study conduct

A list of factors to consider when assessing the relationship of AEs to study conduct is provided in [Appendix 1](#).

The investigator should justify the causality assessment of each SAE.

Relationship of Adverse Events to Injection Procedure, Study Procedure

The relationship of AEs to injection procedure, study procedure, or background treatment, etc. will be assessed by the blinded investigator, and will be a clinical decision based on all available information. The following question will be addressed:

Is there a reasonable possibility that the AE may have been caused by the injection procedure, study procedure, or background treatment, etc.?

The possible answers are:

Not Related: There is no reasonable possibility that the event may have been caused by the injection procedure, study procedure, or background treatment, etc.

Related: There is a reasonable possibility that the event may have been caused by the injection procedure, study procedure, or background treatment, etc.

A list of factors to consider in assessing the relationship of AEs to injection procedure, study procedure, or background treatment, etc. is provided in [Appendix 1](#).

The sponsor will request information to justify the causality assessment of SAEs, as needed.

9.6. Safety Monitoring

The investigator will monitor the safety of study patient at his/her site(s) as per the requirements of this protocol and consistent with current Good Clinical Practice (GCP). Any questions or concerns should be discussed with the sponsor in a timely fashion. The sponsor will monitor the safety data from across all study sites. The medical monitor will have primary responsibility for the emerging safety profile of the compound, but will be supported by other departments (eg, Pharmacovigilance and Risk Management; Biostatistics and Data Management). Safety monitoring will be performed on an ongoing basis (eg, individual review of SAEs) and on a periodic cumulative aggregate basis.

9.7. Investigator Alert Notification

Regeneron (or designee) will inform all investigators participating in this clinical trial, as well as in any other clinical trial using the same investigational drug, of any SAE that potentially meets the relevant requirements for expedited reporting (an AE that is serious, unexpected based on the Investigator's Brochure or this protocol, and has a reasonable suspected causal relationship to the medicinal/study drug).

10. STATISTICAL PLAN

This section provides the basis for the SAP for the study. The SAP may be revised during the study to accommodate amendments to the clinical study protocol and to make changes to adapt to unexpected issues in study execution and data that may affect the planned analyses. The final SAP will be issued before the database is locked at the time of the Group B patients' first step analysis.

10.1. Statistical Hypothesis

Let μ_0 and μ_1 be the population means of the percent change from baseline in calculated LDL-C at week 16 under each of the 2 placebo control arms and the 4 evinacumab treatment arms, respectively. For the primary efficacy variable, the following null hypothesis and alternative will be tested:

$$H_0 : \mu_0 = \mu_1$$

versus

$$H_1 : \mu_0 \neq \mu_1$$

Study treatment route of administration (Group A or B), HeFH diagnosis (Yes/No), and high-intensity statin (Yes/No) (high-intensity statin defined as rosuvastatin 20 mg to 40 mg daily, atorvastatin 40 mg to 80 mg daily, or simvastatin 80 mg daily) will be the 3 stratification factors for patient randomization. Stratification factors HeFH diagnosis and high-intensity statin will be accounted for in the statistical modeling for efficacy.

10.2. Justification of Sample Size

Four pairwise comparisons of evinacumab to a placebo control arm corresponding to the route of administration (Group A or Group B) are hypothesized for the primary efficacy analysis of this study. A total of 216 patients are planned for assessing the primary measure at week 16. Specifically, a sample size of 36 patients per treatment arm will have 90% power to detect a treatment group difference in mean percent change LDL-C of 20% in any 1 pairwise comparison (ie, evinacumab mean = 27% and control mean = 7%), assuming that the common standard deviation (SD) is 25 using an independent group t-test. This sample size has been adjusted for a 5% dropout rate. The alpha level for each of the 4 pairwise comparisons is 0.05 (2-sided), and assumes control of the overall type-1 error rate using a pre-specified hierarchical inferential approach.

Further, the evinacumab 5 mg/kg IV Q4W regimen has been added to Group B, allowing for an assessment of dose-response in the IV route of administration. The additional 36 patients for this second IV dose regimen culminate in a total of 252 patients planned for the study.

With the intent to gain evinacumab experience across these dose regimens for future study planning in patients with HeFH, a subgroup analysis is planned for the stratified sub-population of patients diagnosed with HeFH. To ensure an adequate number of patients are randomized into the HeFH strata level, a total of 175 patients are planned for assessing the percent change LDL-C from baseline at week 16. Specifically, a sample size of 36 patients per treatment arm will have 90% power to detect a treatment group difference in mean percent change LDL-C of 20% in any 1 pairwise comparison (ie, evinacumab mean = 27% and Control mean = 7%), assuming that the common SD is 20 using an independent group t-test. This sample size has been adjusted for a 5% dropout rate.

Blinded Sample Size Adjustment

Referencing the ICH E9 regulatory guidance, the study sample size may be re-estimated after approximately 75% of the patients reach the week 8 visit in the double-blind period, to ensure adequate power in the case of a larger-than-expected variability in the data. This sample size

re-estimation process may be performed twice; once for Group A and again for Group B. The sample size re-estimation will be based on the actual blinded pooled SD (adjusted as described in [Keiser 2003](#)) for the primary efficacy measure. Since the patients' post-baseline LDL-C levels are masked to all study participants (patients, site personnel, and sponsor staff), the blinded pooled SD will be calculated by a designated statistician external to Regeneron who has access to the lipid data. As mentioned in [Kieser 2003](#), the blinded sample size re-estimation does not affect type-I error materially for continuous endpoints.

This re-estimation procedure will assess the need for an increase or decrease in sample size (unrestricted recalculation). The result of this procedure is non-binding, since the decision to increase the sample size will also take into account other study execution factors (for example, availability of patients). In the case the re-estimated sample size is implemented, a protocol amendment will document the modification.

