7.6. Method of Treatment Assignment

Patients will be randomized within either Group A (SC treatment regimens) in a 1:1:1:1 ratio or Group B (IV treatment regimens) in a 1:1:1 ratio. Enrollment of IV cohorts will occur before enrollment of SC cohorts; accordingly, enrollment of Group A will not begin until Group B enrollment is completed. There will be 144 patients randomized to Group A (36 patients per treatment group), with 108 patients exposed to SC evinacumab and 36 exposed to SC placebo. There will be 108 patients randomized to Group B (36 patients per treatment group), with 72 patients exposed to IV evinacumab and 36 exposed to IV placebo.

Patients in Group A will receive treatment from day 1 through week 16 (last dose of study drug at week 15). Patients in Group B will receive treatment from day 1 through week 24 (last dose of study drug week 20). Patients will be randomized to a treatment group according to a central randomization scheme provided by an interactive voice response system (IVRS)/interactive web response system (IWRS) to the designated study pharmacist (or qualified designee).

Randomization will be stratified by study treatment route of administration (Group A or B), high-intensity statin (Yes/No), and HeFH (Yes/No) at baseline. High-intensity statin is defined as rosuvastatin 20 mg or 40 mg daily, atorvastatin 40 mg or 80 mg daily, or simvastatin 80 mg daily (if already on this dose for >1 year). To ensure that an adequate number of patients with HeFH are included, randomization will be stratified 2:1 (HeFH:non-HeFH; 24:12) within each treatment group.

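### The blinded re-estimation may reduce the sample size on the whole-group SD alone, with no check of the separately claimed 90% power in HeFH

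*Protocol*

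**What the plan says.** Protocol 10.2, repeated in SAP 2.2, makes two power statements with the same wording, "a sample size of 36 patients per treatment arm will have 90% power", for a "treatment group difference in mean percent change LDL-C of 20% in any 1 pairwise comparison". The first covers all patients, "assuming that the common standard deviation (SD) is 25 using an independent group t-test". The second covers the HeFH stratum at SD 20 and is introduced with "To ensure an adequate number of patients are randomized into the HeFH strata level", followed by a planned HeFH total of 175. Both allow for 5% dropout.

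HeFH numbers are tied to the total. Protocol 7.6 states that "randomization will be stratified 2:1 (HeFH:non-HeFH; 24:12) within each treatment group".

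The same section then describes an optional blinded re-estimation, once per route group, when about 75% of patients have reached week 8. Its aim is "to ensure adequate power in the case of a larger-than-expected variability in the data". The only statistical input is the blinded pooled SD of the primary measure. On direction, the text says: "This re-estimation procedure will assess the need for an increase or decrease in sample size (unrestricted recalculation"). The result is non-binding, and a change that is implemented is documented in a protocol amendment. Neither document sets a minimum sample size, a minimum HeFH number, or a check of the SD within HeFH.

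**The concern.** The plan rests on two SD assumptions, 25 overall and 20 in HeFH, but the re-estimation tests only the first. A pooled SD below 25 can support a smaller trial, and at a fixed 2:1 ratio every three patients removed from an arm include two HeFH patients. The pooled figure cannot show whether the lower variability arose in HeFH or in non-HeFH patients. If it arose in the non-HeFH patients, the HeFH stratum would shrink although none of its own planning assumptions had changed.

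A decrease also does nothing for the stated purpose, which is protection against too much variability. At stake is the precision of the HeFH estimate, which Protocol 10.2 says is wanted for planning later HeFH studies and which is the reason given for the 2:1 stratification.

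**Working it through.** **Inputs.** Difference 20, SD 25 overall and 20 in HeFH, 90% power and 5% dropout (Protocol 10.2). On alpha: "The alpha level for each of the 4 pairwise comparisons is 0.05 (2-sided"). HeFH share 2/3 (Protocol 7.6). Equal arms.

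**Method.** Two-sample t-test with n evaluable per arm, noncentrality 20 / (SD × √(2/n)), and 2n − 2 degrees of freedom. Randomised number per arm N = n / 0.95, rounded up. Evaluable HeFH per arm = N × (2/3) × 0.95.

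**The plan's own figures.**
- Overall, SD 25: 34 evaluable give 90.2%, and 34 / 0.95 = 35.8, so 36. This reproduces.
- HeFH as printed, 36 per arm at SD 20: 98.7%, or 98.3% with 34.2 evaluable. This does not reproduce.
- What gives 90% at SD 20: 23 evaluable by t-test (22 by normal approximation), so 25 (or 24) randomised. This agrees with 175 / 7 = 25 and, approximately, with 24:12. With 24 randomised, 22.8 are evaluable and power is 91.0%. Seven arms of 24 make 168, not 175.

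**Effect of a decrease.** N is recalculated by the plan's own method at each pooled SD. HeFH power is given after 5% dropout, first with the HeFH SD held at 20, then with it kept at 0.8 of the pooled SD (the planned ratio 20/25).

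| Pooled SD | N per arm | HeFH randomised | HeFH evaluable | Power, HeFH SD 20 | Power, HeFH SD = 0.8 × pooled |
|---|---|---|---|---|---|
| 25 | 36 | 24.0 | 22.8 | 91.0% | 91.0% |
| 24 | 34 | 22.7 | 21.5 | 89.3% | 91.6% |
| 23 | 31 | 20.7 | 19.6 | 86.2% | 91.3% |
| 22 | 29 | 19.3 | 18.4 | 83.8% | 91.7% |
| 21 | 27 | 18.0 | 17.1 | 80.9% | 92.2% |

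**How far a cut can go.** At the look, 75% of 36 = 27 per arm have reached week 8. Patients randomised during the preceding 8 weeks are also already in. The documents give no accrual time and describe no enrolment pause. Assuming steady accrual over T weeks, the fraction already randomised is 0.75 + 8/T.
- T = 32 or less: 36 per arm, so no cut is possible.
- T = 52: 32.5 per arm, 21.7 HeFH, about 88% after dropout at SD 20.
- T = 104: 29.8 per arm, 19.8 HeFH, about 85%.

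Time spent on the calculation and the amendment raises these numbers further.

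**What the low-power case requires.** Ignoring mean differences between strata, pooled variance = (2/3) × HeFH variance + (1/3) × non-HeFH variance. The planned 25 and 20 imply a non-HeFH SD of √(3 × (625 − 266.7)) = 32.8. With HeFH fixed at 20, a pooled SD of 22 requires a non-HeFH SD of √(3 × (484 − 266.7)) = 25.5, and a pooled SD of 21 requires √(3 × (441 − 266.7)) = 22.9.

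**The case against.** Several points on the other side stand.

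- **No cut is forced.** Re-estimation is optional and its result non-binding. A change needs an amendment, and Protocol 15 requires IRB/EC approval of amendments. HeFH numbers could be weighed at that step. However, the text directs nobody to do so, and the execution factors it lists relate only to a decision to increase.
- **The HeFH analysis carries no formal inference.** Its p-value is descriptive (Protocol 10.4.3.4, SAP 5.7.1.3), and it lies outside the testing hierarchy (Protocol 10.4.3.5, SAP 5.7.1.4). The planned HeFH analysis is an interaction MMRM with baseline LDL-C and repeated measures, so a t-test may understate its precision.
- **The loss needs a particular pattern.** HeFH patients make up two thirds of each arm and dominate the pooled SD. For HeFH power to fall as shown, the whole reduction in variability must come from the smaller stratum.
- **Small cuts are nearly harmless.** At 34 per arm, HeFH power is still about 89%.

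A reader might infer that following the rule removes the HeFH power, or that about 81% is the expected result. The documents do not support either: 27 per arm is reached only if nobody is randomised in the 8 weeks before the look, and a proportional fall in the HeFH SD leaves power intact. A reader might also infer that the primary comparisons are weakened. They are not, because the recalculation still targets 90% power at the observed pooled SD, and nothing here bears on the type I error.

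**Conclusion.** The gap is real but modest. Both documents permit a decrease that rests on the whole-group SD, serves no stated purpose, and bypasses the second power claim in the same section. With the HeFH SD at 20, the 2:1 ratio kept and dropout at 5%, HeFH power would go from about 91% to about 86% (31 per arm) or 84% (29 per arm), with 81% as an unlikely limit. Under the assumed 52 to 104 weeks of steady accrual, the lowest reachable value is about 85-88%. If the HeFH SD falls in proportion to the pooled SD, there is no loss.

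The 24 HeFH patients per arm used as the reference come from the 24:12 stratification and from recomputation. The power sentence itself prints 36, which is wrong for 90% at SD 20. That sentence is a separate and certain inconsistency in the same section.

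**What to change.** In Protocol 10.2 and SAP 2.2, do one of the following:

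1. Make the re-estimation increase-only, with the planned 36 per arm as the minimum.
2. Keep the option to decrease, but only when the blinded SD within the HeFH stratum also supports 90% HeFH power at the reduced number.

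Either change takes one sentence in each document and leaves the planned size as it is. Option 1 gives up a possible saving of at most 9 per arm (27 patients in Group B, 36 in Group A), less those randomised in the 8 weeks before the look. Option 2 adds one blinded calculation by the external statistician who already holds the lipid data.

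At the same time, correct the HeFH sample-size sentence in both documents. Replace 36 per arm with the number that gives 90% at SD 20 (24 to 25 randomised), and reconcile the total of 175 (25 per arm) with the 24:12 stratification (168), so that any HeFH minimum refers to a single agreed number.
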